4.2 Treatment Period

During the Treatment Period subjects will receive treatment for up to 24 months or until either disease progression, the occurrence of unacceptable drug-related toxicity or for other reason(s) for subject withdrawal as described in Section 2.1. Subjects should be instructed to immediately inform the Investigator of any AEs. Subjects experiencing dizziness, sleepiness, or other symptoms that could influence alertness or coordination should be advised not to drive or operate other heavy machinery.

Abnormalities in clinical laboratory tests that lead to a change in subject management (e.g., dose delayed [withheld] or reduced, requirement for additional medication, treatment or monitoring) are considered clinically significant and should be documented. If laboratory values constitute part of an CONFIDENTIAL - Cabozantinib + Nivolimab + Ipililumab Protocol Required Elements

event that meets criteria defining it as serious, the event (and associated laboratory values) must be reported as an SAE.

Regular tumor assessments should be performed to determine if PD is present. Tumor assessments should continue on the protocol-defined schedule, relative to the date of first dose of study treatment, regardless of whether study treatment is given, reduced, held or discontinued. The same imaging modalities used at screening will be used for subsequent tumor assessments after first dose.

If the subject is unable to have a study assessment taken within the defined time window due to an event outside of his or her control (e.g., clinic closure, personal emergency, inclement weather, vacation), the assessment should be performed as close as possible to the required schedule.

The Treatment Period ends when a subject receives his or her last dose of study treatment; the subject then enters the Post-Treatment Period.

The following schedule of assessments applies to all subjects. More frequent assessments should be obtained if clinically indicated.

Study Assessments

Study Day/Visit Day	Cycles 1-4 (21 days) Day 1 (+/- 4 days)	Cycles 5 + Day 1 (+/- 4 days)	Instructions
Adverse Event Assessment	Х	Х	
Concomitant Medications	х	х	Review of prohibited medications prior to each study drug dosing
Physical Exam	X	Х	
Vital Signs	х	х	Weight, blood pressure, pulse, 02 saturation, respirations at each visit
ECOG Performance Status	x	x	
Questionnaire(s)	Х	Х	FACT-M (Version 4)
Cabozantinib 40 mg PO daily Continuous	х	х	

CONFIDENTIAL - Cabozantinib + Nivolimab + Ipililumab Protocol Required Elements

Ipilimumab 1 mg/kg IV			
Day 1 Every 3 weeks	X		
(cycles 1-4)			
Nivolumab 3mg/kg IV			
Day 1 Every 3 weeks	X		
(cycles 1-4)			
Nivolumab 480mg IV		x	
Day 1 every 4 weeks		^	
	Refer to	Refer to	Contrast enhanced CT of the chest,
Disease Assessment	instructions for	instructions	abdomen, pelvis.
Disease Assessificit	interval	for interval	Restaging will occur every 12 weeks (+/-1 week)
Cardiac Assessment	х		ECG/EKG – day 1 of cycles 1-4 only
Specimen Collection or	х	x	Serum for banking (4ml lavender top and
Optional Specimen Banking	^	^	4ml red top)
			(prior to treatment start and on treatment
Biopsy	X		for 10 patients) prestudy and on day 15 for
			consenting patients
Complete Blood Count (CBC)	X*	X	See Clinical Safety Laboratory Assessments.
complete blood count (cbc)	^	^	*Repeat CBC/CMP on D14 of cycles 1-4.
Blood Chemistry	X*	x	See Clinical Safety Laboratory Assessments.
blood Chemistry	^	^	*Repeat CBC/CMP on D14 of cycles 1-4.
			See Clinical Safety Laboratory Assessments.
Thyroid Function Tests	X	X	TSH with reflex to free T4 day 1 of odd
			numbered cycles
Tumor Markers			LDH
Immune Parameters	х	х	Immune parameters assessment. Refer to
			Section 4.4
Study Labs Serum Sample			Please see PK section of the protocol.
Pharmacokinetics (PK)			Section 4.4
Urinalysis UPCR	x	x	UA to evaluate for proteinuria
Pregnancy Test (HCG)	х	х	For WOCBP

4.3 Post-Treatment Period

Subjects will return to the study site approximately 30 days after their last dose of treatment to complete end-of-study assessments. Patients will be followed for residual toxicity for 100 days post last day of treatment even if they start a new anticancer therapy. Patients who are removed from study early will be followed for residual toxicity for 100 days post last day of treatment even if they start a new anticancer therapy.

Laboratory and physical examinations will be performed. Remaining study drug will be returned by the subject, and treatment compliance will be documented. Additional follow-up will occur for subjects with AEs related to study treatment that are ongoing at the time of this visit, and for subjects with SAEs related to study treatment that occur after the time of this visit.

Study Day/Visit Day	30 days (+/- 7 days) last study treatment	12 weeks after last study treatment (+/- 14 days)	Instructions
Adverse Event Assessment	х	Х	
Concomitant medications	х	х	
Physical Exam	х	Х	
Vital Signs	х	Х	
ECOG Performance Status	x	х	
Disease Assessment			Contrast enhanced CT of the chest, abdomen, pelvis.
			Restaging will occur every
			12 weeks (+/- 14 days) through
			3 years from the start of
			treatment and then every 6
			months until 5 years from start
			of treatment.

Complete Blood Count (CBC)	х	х	See Clinical Safety Laboratory Assessments.
Blood Chemistry	х	х	See Clinical Safety Laboratory Assessments.
Thyroid Function Tests	х	х	See Clinical Safety Laboratory Assessments.
Tumor Markers	х	х	LDH

4.4 Correlative Studies

Translational studies will be performed on fresh tumor biopsies and peripheral blood specimens and correlated with clinical response to therapy.

- Paired tumor biopsies (pre-treatment and day #15) on 10 subjects with accessible tumors amenable to safe biopsy.
- PBMCs and serum will be collected pre-treatment and on day 1 of each cycle for the first 6 cycles.
- Analysis may include multiplex immunofluorescent tissue staining for characterization of tumor
 infiltrating immune profile, RNAseq to evaluate global gene expression changes within tumor
 resulting from treatment, and characterization of peripheral blood immune cell profiles, T cell
 activation status, and cytokine analysis. Scope of work and budgets will be negotiated with BMS
 and Exelixis separate from this clinical trial protocol.

4.5 Research Participant Registration and Subject Number Assignment Procedures

Research Participant Registration

Patients must meet all of the eligibility requirements and undergo all screening procedures. If a patient enrolls in the study, but does not receive study therapy, the patient's enrollment may be canceled. Reasons for cancellation will be documented in writing. Any patient whose enrollment was canceled before receiving study therapy will be replaced.

Assignment of Subject Numbers

Subject numbers will be assigned at enrollment based on order of enrollment. For example:

- o MFH is the 4th patient enrolled to study. Subject number INC-04
- o B-A is 9th patient enrolled to study. Subject number INC 09

All case report forms, study reports, and laboratory samples for research tests, including immune parameters or pharmacokinetics, will be labeled with the full patient subject number.

Each Consented participant will be assigned only 1 identification number. Numbers must not be reused for different participants. Any participant who is screened multiple times will retain their original identification number.

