2 STUDY OBJECTIVES AND ENDPOINTS

Recent clinical trials have demonstrated median PFS as high as 5 months with the combination of low dose ipilimumab (1 mg/kg IV every 3 weeks) in combination with anti-PD-1 therapies in patients with anti-PD1 refractory cutaneous melanoma. As such, we will use the 5 month mPFS as the benchmark for the design of this clinical trial. In order to show a 4 month improvement in mPFS (with a power of 0.8 and a one-sided test given a type I error rate of 0.05), a total of 41 subjects would need to be enrolled. This signal seeking pilot study will initially enroll 25 subjects at our site (single institution) in less than 2 years. If this treatment combination results in a *mPFS of at least 8 months or an ORR of 45% or higher*, we will review these results with BMS and Exelixis and propose protocol and budget amendments to add 1-2 additional sites to expedite enrollment to a total of at least 41 subjects.

Primary Objective

The primary objective of this clinical trial is to evaluate the clinical efficacy and progression free survival of the triplet combination of ipilimumab + nivolumab + cabozantinib in patients with anti-PD-1/PD-L1 refractory metastatic cutaneous melanoma.

Secondary Objectives:

- Safety/Tolerability (CTCAE v5.0)
- Objective response rate (iRECIST)
- Overall survival
- Correlative translational studies (paired pre-treatment and day #15 on-treatment tumor biopsies for characterization of tumor infiltrating immune cell profiling and gene expression changes)

Primary endpoint:

Progression free survival will be defined as the time between the date of enrollment and the first date of documented progression (per iRECIST), as determined by the investigator, or death due to any cause, whichever occurs first. Cumulative incidence functions will be displayed and summarized for the median time to progression as well as percentage of patients without disease progression at 12, 18, and 24 months.

Secondary endpoints:

- 1. Objective response rate (iRECIST)
- 2. Duration of response
- 3. 6, 12 and 24 month progression free survival
- 4. 12 month overall survival
- 5. Incidence of grade ≥3 treatment related adverse events (CTCAE v5.0)
- 6. Correlative molecular profiling

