4 STUDY ASSESSMENTS AND PROCEDURES

4.1 Pre-Treatment Period

During the Pre-Treatment Period, subjects are consented and qualified (screened) for the study. Informed consent must be obtained before initiation of any clinical screening procedure that is performed solely for the purpose of determining eligibility for this study. Evaluations performed as part of routine care before informed consent can be considered as screening evaluations if done within the defined screening period, and if permitted by the site's institutional review board (IRB)/ethics committee (EC) policies.

Study eligibility is based on meeting all of the study inclusion criteria and none of the exclusion criteria at screening and on Study Day 1 before study treatment administration. The following assessments will be conducted before subjects receive their first dose of treatment on this protocol:

Screening Procedures	Pre-treatment Period Day -28 through initiation of treatment	Instructions
Informed Consent	X	
Medical History	Х	All medical history relevant to the disease under study including smoking history, alcohol use, AJCC M stage, recreational drug use
Adverse Event Collection	Х	
Concomitant Medications	Х	Complete review of current medications with patient including herbal and dietary supplements, and over the counter (OTC)
Comprehensive Physical Exam	Х	To include basic body systems

Vital Signs	Х	Height, weight, blood pressure, pulse, 02 saturation, respiration
ECOG Performance Status	Х	
Disease Assessment	Х	Contrast enhanced CT of the chest, abdomen, pelvis Or MRI abdomen, w/wo gadolinium contrast including non contrast CT are acceptable for patients with iodine contrast allergies.
Cardiac Assessment	Х	ECHO and ECG
Biopsy	х	Optional biopsy prior to initiation of treatment. In patients who do not consent then archival tissue will be requested.
Laboratory Assessments	Х	See Clinical Safety Laboratory Assessments.
Tumor Markers	Х	LDH
Specimen Collection or Optional Specimen Banking	Х	Serum for banking (4ml lavender top and 4ml red top)

For each subject, the Pre-Treatment Period ends upon receipt of the first dose of study treatment or final determination that the subject is ineligible for the study.

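### PFS is timed from enrollment, but undosed patients can be cancelled and replaced and scans run from first dose, so median PFS can be lengthened by an unstated gap (about 0 to 0.46 months if the gap is 0 to 14 days)

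*Combined protocol and SAP*

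**What the plan says.** Three parts of the protocol bear on the time origin.

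- **Endpoint (Section 2, Primary endpoint).** "Progression free survival will be defined as the time between the date of enrollment and the first date of documented progression (per iRECIST"), or to death from any cause if that comes first.
- **Undosed patients (Section 4.5).** For a patient who enrolls "but does not receive study therapy, the patient's enrollment may be canceled". If that is done, replacement is mandatory: "Any patient whose enrollment was canceled before receiving study therapy will be replaced". The same section places enrollment after eligibility has been met and screening completed.
- **Scans (Section 4.2).** "Tumor assessments should continue on the protocol-defined schedule, relative to the date of first dose of study treatment". The interval is given in the assessment table: "Restaging will occur every 12 weeks (+/-1 week"). Section 4.3 also counts later restaging from the start of treatment.

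Section 4.1 requires eligibility to hold "at screening and on Study Day 1 before study treatment administration", so a patient who deteriorates after enrollment may become undosable. Section 8 compares median PFS with a 5-month historical benchmark and sets an expansion criterion, for the first 25 subjects, of median PFS of at least 8 months or ORR of at least 45%. Its Kaplan-Meier estimates use an efficacy evaluable set that is not defined. No section caps the time from enrollment to first dose, and neither Section 2 nor Section 8 states an origin for OS.

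**The concern.** Section 4.5 provides for patients who enroll and are never treated, so enrollment and first dose are separate dates. For a treated patient, the time between them counts as progression-free. The patient must have been alive and still eligible at its end, and no on-study scan is scheduled within it. A patient who dies or deteriorates in that interval can have the enrollment cancelled and the place refilled, in which case the failure need not appear in the endpoint.

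Both features lengthen reported PFS. In a randomized trial they would largely be shared between arms. Here the comparator is a fixed number, so nothing in the design offsets them. At stake are the reported median, the percentages progression-free at the planned landmarks, and the decision to expand beyond 25 patients.

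**Working it through.** **Inputs from the plan.** Benchmark median 5 months, expansion criterion 8 months, 25 patients then 41, scans every 12 weeks from first dose (Sections 2, 4.2 and 8). The 41 cannot be used as a check, because neither its test nor its follow-up is stated and the gap does not enter it.

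**Assumption on the gap.** No figure is given. Enrollment follows screening (Section 4.5). Eligibility laboratory tests (inclusion criterion 8) and QTcF (exclusion criterion 30) must fall within 14 days before first dose. If these are done before enrollment and not repeated, the gap is 0 to 14 days. In months, g = days / 30.4375: 7 days is 0.23 and 14 days is 0.46.

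**Assumption on PFS.** Time X from first dose is exponential with a true median of 5 months, so P(X > x) = 2^(−x/5). Every patient is followed to an event. Reported PFS is X + g.

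**Step 1: median and landmarks.** The reported median is 5 + g: 5.00, 5.23 and 5.46 months for 0, 7 and 14 days. Progression-free at 12 months is 2^(−(12−g)/5): 18.9%, 19.6% and 20.2%.

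**Step 2: 8-month criterion at n = 25, events observed continuously.** The sample median is the 13th ordered time. It reaches 8 months if at most 12 of 25 patients have X below 8 − g. With p = 1 − 2^(−(8−g)/5), the probability is P(Bin(25, p) ≤ 12).

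| Gap (days) | 8 − g | p | P(median ≥ 8) |
|---|---|---|---|
| 0 | 8.00 | 0.670 | 3.8% |
| 7 | 7.77 | 0.659 | 4.9% |
| 14 | 7.54 | 0.648 | 6.3% |

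**Step 3: same criterion, all events dated at scans.** Twelve weeks is 84 / 30.4375 = 2.76 months, so scans fall at 2.76, 5.52 and 8.28 months after first dose. An event found by the second scan is dated no later than 5.52 + 0.46 = 5.98 months, below 8. Any later event is dated at 8.28 months or more, above 8. The criterion is therefore met if at most 12 of 25 events occur by 5.52 months: p = 1 − 2^(−5.52/5) = 0.535, giving about 36% for every gap from 0 to 14 days. The typical observed median still moves, from 5.52 to 5.75 and 5.98 months.

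**Step 4: illustration at n = 41.** The plan names no test. If a one-sample log-rank test were used, with Z = (E − O)/√E, E the events expected under a 5-month median and rejection when Z > 1.645, simulation with full follow-up gives a type I error of about 3.9% with no gap, 5.5% at 7 days and 7.8% at 14 days.

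These steps measure only the shift in the clock. The effect of removing early failures is extra and cannot be sized, because no cancellation rate is given.

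**The case against.** Several points on the other side stand.

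- **Gap length.** The screening window, "Pre-treatment Period Day -28 through initiation of treatment", invites a 28-day gap, which would add 0.92 months and take the illustrative type I error at n = 41 to about 14.5%. The documents do not support that reading. Day −28 is when screening may begin, enrollment comes after screening, and the 14-day limits on laboratory tests and QTcF point to a shorter gap. The 14-day bound is itself an inference, since tests could be repeated after enrollment. With enrollment and first dose on the same day the gap is zero.
- **Event-free by construction.** A reader might infer that everyone analysed is guaranteed to have passed through the interval without an event. The text does not go that far. Cancellation is permitted, not required, so an undosed patient who is kept could contribute an early event, and the efficacy evaluable set is undefined. What remains is that keeping or dropping an early failure is an unregulated choice.
- **Type I error.** It belongs to a test the plan does not contain. At 25 patients the stated rule is the expansion criterion, and its PFS part barely moves when every event is dated at a scan. In that case scan spacing dominates, which is a separate matter.
- **Benchmark.** Its time origin is not given. If it too ran from enrollment with similar exclusions, part of the bias cancels.
- **One shift, not two.** Timing scans from first dose is why the gap carries through to scan-detected events. It is not a second bias to be added.

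None of these removes the mismatch between the clock, the treated population and the scan schedule. They limit its size.

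**Conclusion.** The point holds in a limited form. The PFS origin does not match the scan clock or the cancellation rule, and the mismatch lengthens median PFS for treated patients. The shift is 0 to 0.46 months for an assumed gap of 0 to 14 days, against a 4-month target improvement. With continuously observed exponential PFS and a true median of 5 months, the chance of wrongly meeting the 8-month criterion at n = 25 rises from 3.8% to at most 6.3%; with all events on the scan grid it stays near 36%. Whether the comparison with 5 months is biased by the full amount depends on the benchmark's unstated origin and exclusions. The effect is modest, but its direction is predictable, the design has no control arm to absorb it, and it is easily removed.

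**What to change.** In Section 2, define PFS from the date of first dose and state the same origin for OS. In Section 8, analyse all patients who receive at least one dose, and say whether this is what the efficacy evaluable set means. Report the number of cancelled enrollments with reasons, and the distribution of the enrollment-to-dose interval, so that early failures remain visible. A consistent alternative is to keep the enrollment origin, analyse every enrolled patient without replacement, and count events before dosing.

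The first option changes one phrase in the endpoint definition and adds a sentence or two to Section 8. Sample size, visits and treatment are unaffected. Its downside is that reported PFS is shorter by the gap.

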5 TREATMENT PROCEDURES

5.1 Composition, Formulation, and Storage

All study medication will be stored as described in the appropriate prescribing information for that country (if applicable) or the pharmacy manual and inventoried in accordance with applicable state and federal regulations. Please refer to the most up to date Investigator Brochure in regards to storage conditions, handling, and preparation specifications for all study agents.

5.1.1 Investigational Treatment: Cabozantinib

Cabozantinib tablets are supplied as film coated tablets containing cabozantinib malate equivalent to 20 mg of cabozantinib and contain microcrystalline cellulose, lactose anhydrous, hydoxypropyl cellulose, croscarmellose sodium, colloidal silicon dioxide, magnesium stearate and Opadry® yellow. Cabozantinib 20-mg tablets are round. Doses of 40 mg will comprise two 20-mg tablets. The components of the tablets are listed below.

Cabozantinib Tablet Components and Composition

Ingredient	Function	% w/w ^a
Cabozantinib Drug Substance (25% drug load as free base)	Active Ingredient	31.68
Microcrystalline Cellulose (Avicel® PH-102)	Filler	38.85
Lactose Anhydrous (60M)	Filler	19.42
Hydroxypropyl Cellulose (EXF)	Binder	3.00
Croscarmellose Sodium (Ac-Di-Sol®)	Disintegrant	6.00
Colloidal Silicon Dioxide	Glidant	0.30
Magnesium Stearate	Lubricant	0.75
Opadry® yellow film coating which includes HPMC 2910/hypromellose 6 cp, titanium dioxide, triacetin, and iron oxide yellow	Film Coating	4.00
^a weight fraction, expressed in percentage; HPMC, hydroxypropyl methylcellulose		

Refer to the Pharmacy Manual for details on storage and handling of cabozantinib.

5.1.2 Nivolumab

Nivolumab is a soluble protein consisting of 4 polypeptide chains, which include 2 identical heavy chains and 2 identical light chains. Nivolumab is produced from cell culture using a CHO cell line. The physical and chemical properties of nivolumab drug substance are provided below:

Physical and Chemical Properties of Nivolumab Drug Substance

BMS Number BMS-936558-01

Other Names nivolumab, BMS-936558, MDX1106, ONO-4538, anti-PD-1

Molecular Weight 146,221 daltons (143,619.17 daltons, protein portion)

Appearance Clear to opalescent, colorless to pale yellow liquid, light (few) particulates may be present Solution pH 5.5 to 6.5

Refer to the Pharmacy Manual for details on storage and handling of nivolumab.

5.1.3 Ipililumab

Ipilimumab (BMS-734016, MDX-010) is a fully human IgG1② consisting of 4 polypeptide chains; 2 identical heavy chains primarily consisting of 447 amino acids each with 2 identical kappa light chains consisting of 215 amino acids each linked through inter-chain disulfide bonds. Ipilimumab is produced from cell culture using a Chinese Hamster Ovary (CHO) cell line. The physical and chemical properties of the ipilimumab drug substance are provided below:

Physical and Chemical Properties of Ipilimumab Drug Substance

BMS Number BMS-734016-01 or BMS-734016

Other Names/Laboratory Codes Yervoy®, MDX-010, MDX-CTLA-4

Molecular Weight 147,991 Daltons

CONFIDENTIAL - Cabozantinib + Nivolimab + Ipililumab Protocol Required Elements

Appearance Clear to slightly opalescent, colorless to pale yellow liquid, may contain particles Solution pH 7.0

pl The isoelectric focusing analysis generates a banding pattern in the pl range of 8.5 to 8.8, with the major isoform at an approximate pl of 8.7

Abbreviations: pI = isoelectric point.

Refer to the Pharmacy Manual for details on storage and handling of nivolumab.

5.2 STUDY TREATMENT ADMINISTRATION

5.2.1 **Cabozantinib Administration**

Subjects will receive cabozantinib orally at a (starting) dose of 40 mg once daily.

Cabozantinib tablets should only be taken whole by mouth and should not be cut, chewed, or crushed for dissolving in liquid or administered through other routes including percutaneous endoscopic gastrostomy (PEG) tubes. Cabozantinib tablets should not be administered to subjects who do not have adequate swallowing capacity. Cabozantinib should not be taken with food (subjects should not eat for at least 2 h before and at least 1 h after taking cabozantinib) and should be taken with a full glass (at least 8 ounces or 240 mL) of water. If a dose is missed, the missed dose should not be taken less than 12 h before the next dose. Cabozantinib tablets should be stored at controlled room temperature and inventoried according to applicable regulations

In all subjects, dose reductions and delays to manage toxicity are allowed under the guidelines in Section 5.4 below.

5.2.2 **IO Therapy Administration**

Participants will be treated with ipilimumab 1 mg/kg and nivolumab 3 mg/kg every 3 weeks for 4 cycles. For cycles 5+, treatment will consist of nivolumab 480 mg IV every 4 weeks. The total duration of therapy will be 24 months.

5.3 **Study Treatment Accountability**

The Investigator or designee will maintain accurate records of receipt of all study treatment including dates of receipt. In addition, accurate records will be kept regarding the date, lot number, and how CONFIDENTIAL - Cabozantinib + Nivolimab + Ipililumab Protocol Required Elements

much study treatment is dispensed and used by each subject in the study. Reasons for deviation from the expected dispensing regimen must also be recorded. At completion of the study, to satisfy regulatory requirements regarding drug accountability, all unused study treatment will be reconciled and destroyed according to applicable state, federal, and local regulations.

Drug accountability records will be maintained by the Providence Health & Services Oregon Region Investigational Drug Services pharmacy.

Unused investigational drug will be returned or destroyed at study close or when drug expires as per the site's policy.

At the end of the study period, Bristol-Myers Squibb Company will not continue to supply study drug (Nivolumab and Ipilimumab) to subjects/investigators unless the Sponsor-Investigator chooses to extend their study. The investigator is responsible to ensure that the subject receives appropriate standard of care or other appropriate treatment in the independent medical judgement of the Investigator to treat the condition under study."

All investigational drug accountability records, physical inventory and other supporting documents (such as temperature monitoring logs) will be made available to the monitor and applicable regulatory agencies for auditing and monitoring purposes.

